# **Protocol Synopsis**

· · · · · · · · · · · · · · · · · · ·	ГП
	In this study, progression free survival (PFS) based on independent radiologic review is the primary efficacy indicator and RECIST v1.1-GIST Specific Standard is used for tumor efficacy assessment.
	After being fully informed, signing the informed consent forms and passing the screening, the subjects will receive DCC-2618 (150 mg, QD) continuously until the occurrence of an event for treatment termination as specified in the protocol, 28 days as a treatment cycle, followed by a safety follow-up period until 30 days after the termination of study treatment.
	During the study period, the subjects will be subject to visits as scheduled in the protocol. On the day of the scheduled visit as per the protocol, the subjects should bring the drug to the study site, where they will complete all the pre-dose examinations, and take the drug of the day after being suitable to continue the administration, in the discretion of the investigator. In the first four cycles (inclusive), an radiographic examination will be performed within $\pm 7$ days of each cycle and tumor efficacy will be assessed according to RECIST v1.1-GIST Specific Standard. After that, it should be performed within $\pm 7$ days every two cycles.
	If the subject discontinues treatment for reasons other than progressive disease, death, withdrawal of informed consent and lost to follow-up, the subject should receive radiographic examination for tumor assessment by independent radiologic review (IRR) after treatment withdrawal according to the frequency consistent with that during the study until presence of disease progression meeting "RECIST v1.1-GIST Specific Standard" or until starting of new anti-tumor therapy, whichever is the first.
	Based on independent radiologic review, if a subject has a radiologically confirmed progression disease (PD), the subject can choose:
	• To continue DCC-2618, at an increased dose of 150 mg BID, until the occurrence of an event for treatment termination as specified in the protocol; in the case of the efficacy evaluation for such patient, the lesion diameter before the increase of dosage (but not screening period) should be taken as the baseline value.

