#### Figure 1 Study Diagram

Note: Based on IRR, continued treatment with an increase to 150 mg BID or with the original dosage should not be provided for a patient after the first PD, unless he or she is evaluated by the Investigator as able to tolerate. The diameter of the lesion before the increase of dosage (other than that during the Screening Period) should be used as baseline diameter when the effect on the patient after dose up-titration is evaluated.

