- To continue DCC-2618, at an increased dose of 150 mg BID, until the occurrence of an event for treatment termination as specified in the protocol; in the case of the efficacy evaluation for such patient, the lesion diameter before the increase of dosage (but not screening period) should be taken as the baseline value.
- To continue DCC-2618 at a dose of 150 mg QD, until the occurrence of an event for treatment termination as specified in the protocol, if the subject can benefit from the treatment with DCC-2618, but cannot tolerate the increase of dosage, after being fully assessed by the investigator;
- To terminate the treatment with DCC-2618.

After subjects are enrolled into the study, PK blood samples will be collected according to the time specified in the protocol.

After PK sampling, the subjects can continue the treatment with DCC-2618, safety visits and

efficacy evaluation, until the occurrence of an event for treatment termination as specified in the protocol.

Treatment suspension or dosage reduction or treatment withdrawal is allowed at any time during the study for subjects with an intolerant toxicity reaction.

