## 5.2.1 Dose escalation

DCC-2618 will be continued after the subject has radiologically confirmed disease progression based on independent imaging review and the dose was escalated to 150 mg twice daily (BID) until the protocol-specified event of treatment discontinuation; For the assessment of efficacy in this part of patients, the diameter of the lesion before dose escalation (not at screening) should be used as the baseline diameter.

On the basis of independent radiology review, when subjects experience disease progression, they should be informed of other optional treatments.

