## 5.3.2 Dose interruption and dose reduction due to adverse events

Treatment suspension and/or dosage reduction of the investigational drug or treatment termination will be allowed at any time during the study for subjects with an intolerant toxicity reaction of any levels. If the drug is resumed after dose suspension, calculation of visit cycle should be based on the predetermined arrangement and not influenced by dose suspension. See Table 6 for dose adjustment regimen.

If subjects can't tolerate 50 mg QD or experience disease progression based on independent radiology review after dose reduction, the study treatment should be terminated and subjects should enter the safety follow-up period and start survival follow-up.

All dose interruptions, reductions (including missed doses), downtitration, or uptitration, and reasons must be recorded on the eCRF form.

	Initial dose	First reduction	Second reduction
Initial Patient	150mg QD	100mgQD	50mg QD
Patients whose dosage are increased to 150 mg BID after disease progression	150mg BID	100mgBID	150mg QD

 Table 6 DCC-2618 Dose Modification Scheme

If the adverse event resolves to grade 1 or baseline level and the drug is resumed, the subject will be allowed to resume the drug at the dose when the adverse event occurred. If the dose

for the subject has been reduced to the first reduced dose and the adverse event resolves to grade 1 or baseline level, the subject will be allowed to resume the drug at the initial dose. If the subject has experienced two consecutive reductions and the adverse event resolves to grade 1 or baseline level, the subject will be only allowed to resume the drug at the first reduced dose for at least one cycle (28 days) continuously and then use the drug at the initial dose.

If the adverse event does not resolve to grade 1 or baseline level within 28 days, the study treatment should be discontinued, unless the investigator evaluates that the adverse event is not clinically significant. After discussing with the sponsor, there may be an opportunity to resume the drug at a dose reduced by one level.

dose adjustmen							
Severity of AE	Handling of AE and dose adjustment principles						
Grade 1	Provide symptomatic and supportive treatment, and continue the drug at the original dose.						
Grade 2	Provide symptomatic and supportive treatment, and continue the drug at the origin dose.						
	If the AE is not improved within 7 days, the treatment should be withheld:						

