Independent imaging supplier must ensure independent radiology reviewers are blinded to investigator's assessment and other information. Before any independent radiology review, this procedure and all other radiographic images procedures will be recorded in the specified review rules of protocol between the sponsor and the independent imaging supplier.

Independent radiology reviewers and investigators will assess tumor response based on RECISTv1.1-GIST Specific Standard. Response confirmed by investigators will be recorded in the eCRF. Data from independent radiology review will be used for primary endpoint analysis.

**Confirmation of absence of progressive disease:** if independent radiology reviewers confirm there is no progressive disease, the patient will continue to receive treatment with the investigational drug, unless there are medical needs requiring discontinuation of the investigational drug (that is, rapid progression or clinical worsening). If investigators confirm progressive disease according to clinical worsening, scan should be performed and reviewed by independent radiology reviewers to confirm whether the patient has progression. Basis of confirming progressive disease as per clinical worsening should be recorded in patients' source documents and eCRF.

**Confirmation of progressive disease:** subjects who have radiologically confirmed progressive disease on the basis of independent radiology review can continue DCC-2618 treatment at a dose increased to 150 mg, BID; subjects who can benefit from DCC-2618 treatment but cannot tolerate the increased dose will continue DCC-2618 treatment, 150 mg QD; or discontinue DCC-2618 treatment. If subjects use the drug at the original dose, dose escalation will not be performed in the future.

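### A patient on a reduced dose (100 mg or 50 mg QD) at first IRR progression must stop under Section 5.3.2 but is escalated or may continue under other sections, and no text says which rule controls

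*Combined protocol and SAP*

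**What the plan says.** **The stop rule.** Section 5.3.2 covers two kinds of subject: those who cannot tolerate 50 mg QD, and those who "experience disease progression based on independent radiology review after dose reduction, the study treatment should be terminated". Both go to safety and survival follow-up. Table 6 gives the initial ladder as 150, 100 and 50 mg QD.

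**The continuation rules.** The synopsis and Section 3.1 open with "if a subject has a radiologically confirmed progression disease (PD), the subject can choose" and list three options:
- continue "at an increased dose of 150 mg BID, until the occurrence of an event for treatment termination as specified in the protocol";
- continue at 150 mg QD "if the subject can benefit from the treatment with DCC-2618, but cannot tolerate the increase of dosage, after being fully assessed by the investigator";
- stop the drug altogether.

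Section 6.10.1 permits 150 mg BID and then says that "subjects who can benefit from DCC-2618 treatment but cannot tolerate the increased dose will continue DCC-2618 treatment, 150 mg QD; or discontinue DCC-2618 treatment". Section 5.2.1 is firmer: treatment goes on after IRR-confirmed progression and "the dose was escalated to 150 mg twice daily (BID) until the protocol-specified event of treatment discontinuation".

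**The investigator conditions.** The Figure 1 note rules out continued treatment after first progression, at BID or at the original dosage, "unless he or she is evaluated by the Investigator as able to tolerate". Section 8.1 discontinues subjects whom the investigator finds unsuitable for escalation or for staying on the original dose. Neither mentions an earlier dose reduction.

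**The concern.** A patient whose dose was cut for toxicity and who then progresses falls under two sets of rules. One ends treatment. The other leads to, or allows, a dose above the one the patient is taking. With about 10 sites (Section 3.2), different sites could follow different sections and each be complying with the text.

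Two things turn on the choice. The first is post-progression exposure, and so safety, in patients who have already needed a reduction. Section 1.4.2.1.4 describes 100 mg QD as the level for a patient who cannot tolerate 150 mg QD. Table 6 gives the BID ladder as 150 mg BID, 100 mg BID, 150 mg QD, so an escalated patient has no listed step back to 100 mg or 50 mg QD. The second is who enters the exploratory PFS2 analysis and the BID safety data, because PFS2 starts at the first 150 mg BID dose (Section 9.4.5.4).

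The phrase *after dose reduction* is also open. Section 5.3.2 lets patients return to 150 mg QD once the adverse event resolves, and does not say whether such a patient must still stop at progression.

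**Working it through.** The plan states no figure on this point, so there is none to reproduce. The check is a comparison of texts, followed by simple dose ratios.

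**Step 1: which progression does 5.3.2 mean?** The sentence names 50 mg QD, which is on the initial ladder in Table 6 but not on the BID ladder. It relies on IRR, whereas Section 8.1 assigns progression after escalation to BID to the investigator. The stop rule therefore covers first progression in patients reduced to 100 mg or 50 mg QD.

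**Step 2: the same patient under each section.** Take a patient on 100 mg QD at first IRR progression who wants to continue and whom the investigator judges able to tolerate 150 mg BID.

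| Place | Result |
|---|---|
| 5.3.2 | Terminate |
| 5.2.1 | Escalate to 150 mg BID |
| Synopsis, 3.1, 6.10.1 | 150 mg BID permitted; 150 mg QD if benefiting but unable to tolerate the increase; termination also listed |
| Figure 1 note, 8.1 | No bar, because the investigator's judgement is favourable |

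If the patient prefers to stop, or the investigator judges continuation unsuitable, stopping fits 5.3.2, 3.1 and 8.1. The conflict is confined to the patient described.

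**Step 3: size per patient.** Ratio = daily dose offered / current daily dose, with 150 mg BID = 300 mg a day.
- From 100 mg QD: 150/100 = 1.5; 300/100 = 3.0.
- From 50 mg QD: 150/50 = 3.0; 300/50 = 6.0.

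Table 5 (Section 1.4.2.1.3) gives model-predicted combined AUC over 24 hours (ng·h/mL): 22,389 at 100 mg QD, 33,583 at 150 mg QD and 67,098 at 150 mg BID.
- 33,583/22,389 = 1.50; 67,098/22,389 = 3.00.
- 50 mg QD is not in Table 5. Assuming dose proportionality, which Section 1.4.2.1.3 reports, exposure is 33,583/3 = 11,194. Then 33,583/11,194 = 3.00 and 67,098/11,194 = 5.99.
- For comparison, a full-dose patient going from 150 mg QD to 150 mg BID: 67,098/33,583 = 2.00.

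**Step 4: limit on the 50 mg figures.** After two reductions, 5.3.2 lets a patient resume only at the first reduced dose, for at least one 28-day cycle, before the initial dose. A direct step from 50 mg QD to 150 mg QD or BID does not fit that rule, so the 3-fold and 6-fold ratios are nominal.

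**The case against.** The strongest reply is that the texts can be reconciled. The wording about continuing until a termination event governs initial treatment as well as the options. Section 5.3.2 can be read as defining such an event, so a reduced patient's treatment ends before the option list is reached. The options also seem written with full-dose patients in mind: they speak of continuing at 150 mg QD or at the original dose, and none offers 100 mg or 50 mg QD. On this view 5.3.2 is the specific rule, 3.1 is an overview, and only a cross-reference is missing.

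That is plausible and may well be what the sponsor intended, but no text says it. The opening of the option list covers any subject with IRR-confirmed progression, the BID option is not limited to full-dose patients, and 5.2.1 is itself the dedicated section on escalation. Attached to an option, the termination-event wording limits how long that option lasts, not who may choose it.

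Other parts of the reply stand. Termination is a listed choice in the synopsis, 3.1 and 6.10.1, and only 5.2.1 directs continuation. The investigator conditions will stop some reduced patients. A step from 100 to 150 mg QD is one that 5.3.2 itself allows once the adverse event resolves. Phase 1 evaluated 150 mg BID without reaching an MTD (Section 1.3.1), so BID is not an untested dose.

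**Conclusion.** The protocol is wrong as written on this point. For a patient on 100 mg or 50 mg QD at first IRR progression, 5.3.2 terminates, 5.2.1 escalates, three other places permit continuation, and nothing ranks them. The weight is minor to moderate; the plan should be corrected, but the main result does not depend on it.

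The size is per patient: 1.5-fold or 3-fold the current daily dose from 100 mg QD, and nominally 3-fold or 6-fold from 50 mg QD. The 50 mg exposure figures rest on assumed dose proportionality. The documents give no dose-reduction rate, so no patient count can be stated.

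A reader might infer three stronger things that the documents do not support:
- *That the protocol as a whole forces toxicity-reduced patients to escalate.* Only 5.2.1 directs it, and the Figure 1 note and 8.1 make continuation depend on the investigator.
- *That the primary analysis is compromised.* IRR PFS ends at first IRR progression or death, before this choice arises.
- *That a direct 6-fold step from 50 mg QD is prescribed.* The re-escalation rule in 5.3.2 points the other way.

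**What to change.** Let the sponsor's own stop rule control.

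1. In the synopsis, Sections 3.1, 5.2.1 and 6.10.1 and the Figure 1 note, add: *except subjects whose dose is reduced to 100 mg or 50 mg QD at IRR progression, who terminate treatment under Section 5.3.2*.
2. In 5.3.2, replace *after dose reduction* with *while the dose is reduced to 100 mg or 50 mg QD*. Patients already restored to 150 mg QD then keep the 3.1 options, subject to the existing investigator assessment. The sponsor should confirm that this is intended.
3. If temporary holds are addressed, class a held patient by the dose level at which Tables 7 to 9 would allow the drug to be resumed, not by the last level assigned. A patient held from 150 mg QD for a Grade 3 skin or joint/muscle event must resume lower (Table 7), and Table 9 requires a one-level reduction after most other Grade 3 or 4 events. Classing by the last assigned level would leave the BID option open to such patients.

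The cost is a protocol amendment, with Ethics Committee approval before implementation (Section 10.4). Patients on a reduced dose lose the continuation option that 3.1 now offers. This is a design decision for the sponsor. No new data are needed, since 5.3.2 already requires dose changes and their reasons in the eCRF.

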	• If the AE resolves to grade 1 or baseline level within 7 days, the drug can be resumed at the original dose;						
	• If the AE resolves to grade 1 or baseline level within 7 days, the drug can be resumed at a lower dose level;						
	If the AE occurs for the second time, regardless of the time of resolving to grade 1 or baseline level, the drug can be resumed at a lower dose level.						
	After reducing the dose, if AE remains grade 1 or baseline level for at least 2 consecutive cycles (56 days), the dose can be increased by one level.						
Grade 3	Symptomatic and supportive treatment						
	Withhold the invstigational drug for at least 7 days or until the AE resolves to grade 1 or baseline level (28 days at most).						
	• Resume medication at a lower dose level.						
	After reducing the dose, if AE remains grade 1 or baseline level for at least 2 consecutive cycles (56 days), the dose can be increased by one level.						
Grade 4	Discontinuation of study treatment. After the investigator evaluates and discusses with the sponsor, for non-life-threatening adverse events, medication can be continued.						
Any Grade	Stevens-Johnson syndrome						
	If patients have Stevens-Johnson syndrome (SJS), the investigational drug must be discontinued permanently. Patients should be sent to hospital immediately to receive clinical assessment and supportive treatment according to institutional guidance. Because there is risk of recurrence of SJS, the investigational drug should not be administered again.						

Table 7 Handling of dermatological toxicity and joint pain/myalgia and principles of dose adjustment

Severity of AE	Handling of AE and dose adjustment principles*
Grade 1 (systolic BP 120-139 mmHg,	Start blood pressure monitoring;
diastolic BP 80-89 mmHg)	The original dose was continued.

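### Table 7 gives two different resumption doses for the same Grade 2 recovery, and leaves a slower first recovery to general text that allows the full dose

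*Combined protocol and SAP*

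**What the plan says.** Table 7 covers dermatological toxicity and joint pain/myalgia. In its Grade 2 row, dosing first continues with supportive care, and then: "If the AE is not improved within 7 days, the treatment should be withheld". Two bullets follow on how to restart. The first: "If the AE resolves to grade 1 or baseline level within 7 days, the drug can be resumed at the original dose". The second: "If the AE resolves to grade 1 or baseline level within 7 days, the drug can be resumed at a lower dose level". The next line deals with a second occurrence, for which, "regardless of the time of resolving to grade 1 or baseline level, the drug can be resumed at a lower dose level".

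The general text of 5.3.2, ahead of the tables, is not limited by grade or type of event. On recovery to grade 1 or baseline, "the subject will be allowed to resume the drug at the dose when the adverse event occurred". It also sets an outer limit: "If the adverse event does not resolve to grade 1 or baseline level within 28 days, the study treatment should be discontinued". There is an exception where the investigator judges the event not clinically significant; after discussion with the sponsor, restart one level lower may then be possible.

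**The concern.** A site that follows the Grade 2 row for a first event with recovery inside 7 days finds two answers and no rule for choosing between them. Two patients with the same course could restart at different doses, both in line with Table 7. A site whose patient recovers more slowly finds nothing in the row.

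The row is likely to be used. All-grade rates in the phase 1 study were 34.4% for myalgia and 30.9% for palmar-plantar erythrodysesthesia (section 1.3.1.1.1); myalgia was 31.8% on ripretinib in the phase 3 study (section 1.3.1.1.2). These are not Grade 2 rates, so they do not give the number of patients affected. About 35 patients at about 10 sites leave each site with few cases from which to form a consistent habit.

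What is at stake is dosing after toxicity. In the analysis, the descriptive count of adverse events leading to dose reduction or adjustment could shift, because the bullet a site follows can decide whether an event is counted.

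**Working it through.** No statistic in the plan depends on this wording, so the check is a comparison of the branches, followed by the size of one dose level.

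**Branches after withholding for Grade 2 (Table 7, with doses from Table 6 for a patient on the starting dose)**

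| Course | Table 7, Grade 2 | Dose allowed |
|---|---|---|
| First event, recovery within 7 days | two bullets, same condition | 150 or 100 mg QD |
| First event, recovery after 7 days | no line; general text of 5.3.2 applies, limit 28 days | 150 mg QD |
| Second event, any recovery time | lower level | 100 mg QD (if the first restart was at 150) |

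For a patient escalated to 150 mg BID, Table 6 gives 150 or 100 mg BID in the first line.

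**What the row implies.** The second-occurrence line applies whatever the recovery time. That qualifier makes sense only if time was meant to separate the two bullets above it. The likely reading is fast recovery, original dose; slow recovery, lower dose. As written, the result runs the other way: the lower dose is offered to some fast recoveries, while slow recoveries fall to the permission to restart at full dose.

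**When the 7 days start.** The row uses 7 days twice, once as the trigger for withholding and once for recovery, and gives no starting day for the second. If both ran from onset, an event that reached withholding would already have gone 7 days without improvement, and neither bullet could ever apply. The start of withholding is therefore the workable reading, but it is not stated.

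**Size of one dose level (Table 5, predicted combined AUC over 24 h, ng·h/mL)**

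- QD: 33,583 / 22,389 = 1.50
- BID: 67,098 / 44,732 = 1.50

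**Cost in the other direction (section 1.4.2.1.3, simulated share above 10,000 ng·h/mL)**

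- 150 mg QD 93.6%; 100 mg QD 87.9%; difference 93.6 − 87.9 = 5.7 percentage points
- Share below threshold: 100 − 93.6 = 6.4% against 100 − 87.9 = 12.1%

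**The case against.** **The bullets are permissive.** Each says the drug can be resumed, and 5.3.2 opens by allowing reduction at any time for intolerable toxicity of any grade. Neither dose is unauthorised, and after a correction two sites could still differ on clinical judgement. This stands, and it limits the harm. It does not supply the missing default rule.

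**Slow recovery is not without a rule.** A reader might infer that the protocol gives no dose for it. The general text does, up to 28 days. The gap is in Table 7 only; the trouble is that the rule filling it is probably the opposite of the intended one.

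**It may be a translation slip.** The abbreviation list is headed as Chinese terminology, a Chinese label remains in Table 5, and Table 3 labels as QD dose groups that section 1.3.1 lists as BID. Whether sites worked from this English wording cannot be known from the documents. That is a reason to check the source-language text. A repeated clause is still unlikely to come from PDF extraction.

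**A lower dose has a price.** The simulated share under the threshold nearly doubles, and section 1.4.2.1.4 warns about doses under 150 mg. The same section also says a patient who cannot tolerate 150 mg QD can go to 100 mg QD without loss of efficacy. Both belong in the medical team's decision.

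**A wider conflict is tempting to infer.** The general text allows the same dose on recovery, while Table 7 Grade 3 and the first row of Table 9 require a lower level; the waits before re-escalation also differ. The documents do not support calling this a contradiction. Specific rows ordinarily govern, the general text only permits, and different toxicities may reasonably have different waits. It is at most a clarity gap.

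**Conclusion.** The Grade 2 row of Table 7 is wrong as written: one condition, two doses, and no line for a slower first recovery. The consequence is one dose level, 1.5-fold in predicted combined AUC, for a first Grade 2 skin or joint/muscle event that did not improve in 7 days, was withheld and then recovered. The context is reassuring: 150 mg QD is the recommended dose, no maximum tolerated dose was reached in escalation, and recovery to grade 1 or baseline comes before restart. For patients on 150 mg BID there is less comfort, since section 1.4.2.2 itself raises tolerability after escalation.

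The view that time was meant to separate the bullets is an inference from the line that follows them, though a strong one. A reader might also infer an effect on progression-free survival or on the sample size. Nothing in the documents supports that: neither depends on this rule, and the number of patients affected is unknown. This is a minor safety-conduct correction.

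**What to change.** Change the condition of the second Grade 2 bullet in Table 7 to recovery to grade 1 or baseline after more than 7 days and within 28 days, and keep its consequence, a lower dose level. In the same edit, state that the 7 days are counted from the start of withholding, or from whatever day the medical team confirms. The medical team should check both against the source-language protocol first.

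Do not add a blanket clause applying the 28-day recovery rule to every table. Table 9 allows restart once certain laboratory events fall to grade 3 and does not require withholding for asymptomatic CPK or lipase rises. In Table 8, hypertension controlled with added drugs may not return to grade 1.

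The cost is one corrected bullet in a protocol amendment, with ethics committee approval before use (section 10.4), and a memo to sites. Some slow recoveries will restart at 100 mg QD, with the 5.7-point lower simulated threshold attainment shown above. Sample size and analyses do not change.

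### Table 7, Grade 3 row: as worded, a Grade 3 skin or joint/muscle event can be re-dosed at a lower level from day 7 without having recovered

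*Combined protocol and SAP*

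**What the plan says.** Protocol Section 5.3.2, Table 7, sets the dose rules for dermatological toxicity and joint pain/myalgia.

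- **Grade 3, hold:** "Withhold the invstigational drug for at least 7 days or until the AE resolves to grade 1 or baseline level (28 days at most").
- **Grade 3, restart:** "Resume medication at a lower dose level". No condition is attached to this step.
- **Grade 2, hold:** dosing continues at first, with symptomatic treatment. "If the AE is not improved within 7 days, the treatment should be withheld".
- **Grade 2, restart:** two bullets, "If the AE resolves to grade 1 or baseline level within 7 days, the drug can be resumed at the original dose" and "If the AE resolves to grade 1 or baseline level within 7 days, the drug can be resumed at a lower dose level".
- **Grade 4:** treatment stops, with one exception: "After the investigator evaluates and discusses with the sponsor, for non-life-threatening adverse events, medication can be continued".
- **Re-escalation (Grades 2 and 3):** the condition begins "After reducing the dose, if AE remains grade 1 or baseline level for at least 2 consecutive cycles".

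The general text of Section 5.3.2 covers two situations. One begins "If the adverse event resolves to grade 1 or baseline level and the drug is resumed". The other is an event unresolved at 28 days: treatment stops unless the investigator judges the event not clinically significant, and resumption one level down may be possible after discussion with the sponsor. Section 5.3 limits any interruption for toxicity to 28 consecutive days.

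**The concern.** Joined by *or*, either limb of the Grade 3 instruction is enough to end the hold. Seven days off drug would satisfy it even if the event is still Grade 3, and the restart bullet adds no further test. Two sites could restart the same kind of patient on different days and both be following the text. One of them would be re-dosing an unrecovered Grade 3 event without having to consult the sponsor.

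The row is also out of step with its surroundings. Grade 3 is otherwise handled more strictly than Grade 2: the hold is immediate and the lower dose is mandatory. Only the release condition is looser. These event types were common in earlier studies. All-grade myalgia was 34.4% and palmar-plantar erythrodysesthesia 30.9% in the phase 1 study (Section 1.3.1.1.1). In the randomized phase 3 study, myalgia was 31.8% against 11.6% on placebo (Section 1.3.1.1.2).

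**Working it through.** The plan states no figure to reproduce. The check is a reading of the text, plus simple arithmetic on the gap between the two readings.

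**Step 1. Does any other text close the gap?**

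| Place | Effect on an unresolved Grade 3 event at day 7 |
|---|---|
| Section 5.3, 28-day limit on interruption | Acts only at day 28 |
| Section 5.3.2, resumption paragraph | Describes restart after resolution; does not forbid earlier restart |
| Section 5.3.2, 28-day rule | Acts only at day 28 |
| Sections 5.3 and 5.3.2, freedom to suspend, reduce or stop | Permits caution; does not require it |

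None of these bars the day-7 restart.

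**Step 2. How do neighbouring rules treat recovery?** The Grade 2 bullets of Table 7 and the first row of Table 9 (Grade 2 weight loss and other Grade 3 or 4 events) tie restart to recovery to Grade 1 or baseline. The Grade 2 bullets are themselves faulty, because one condition leads to two different doses. They are used here only to show that recovery is required. Recovery is not required everywhere: the Grade 4 exception and the 28-day rule both leave room for dosing without it, but both refer to discussion with the sponsor. The literal Grade 3 restart does not.

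**Step 3. What was probably meant?** Four features point to recovery being required:

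- the 7 days are expressed as a minimum;
- the 28-day cap would do little if 7 days alone ended the hold;
- the re-escalation line speaks of the event *remaining* at Grade 1 or baseline, which presupposes that it got there;
- the general text links resumption to resolution.

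**Step 4. How far apart are the readings?** Let r be the day of recovery, from 1 to 28.

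- Under *or*: earliest restart = min(r, 7).
- Under *and*: earliest restart = max(r, 7).
- Difference = max(r, 7) − min(r, 7) = |r − 7|.

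| Recovery day r | Under *or* | Under *and* | Difference (days) |
|---|---|---|---|
| 1 | 1 | 7 | 6 |
| 3 | 3 | 7 | 4 |
| 6 | 6 | 7 | 1 |
| 7 | 7 | 7 | 0 |
| 8 | 7 | 8 | 1 |
| 14 | 7 | 14 | 7 |
| 21 | 7 | 21 | 14 |
| 28 | 7 | 28 | 21 |

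The rows with r above 7 carry the safety issue, since there the literal reading allows dosing before recovery. For an event unresolved at day 28, *and* leads to the 28-day rule.

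**Step 5. How many subjects?** This cannot be derived. The incidence rates quoted above are for all grades, and the documents give no Grade 3 rate or recovery time for Table 7 events.

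**The case against.** The best answer is that no sensible investigator would read the row this way. A minimum hold is not an instruction to restart, and Section 5.3.2 describes resumption either after resolution or at the 28-day point, with no route in between. An unconditioned second bullet is also the tables' usual format: in Table 9's first row, the dose-reduction step carries no condition either. Other rows tolerate dosing with unresolved Grade 3 findings. Table 8 specifies a hold for Grade 3 hypertension only if there are symptoms, and Table 9 continues the original dose for asymptomatic Grade 3 or 4 laboratory abnormalities lasting up to 10 days. The text also shows signs of translation, so the *or* may be a slip absent from the wording used at sites.

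Much of this stands as evidence of intent: recovery is the likelier meaning. But that supports correcting the row, because its words do not say so. The hypertension and laboratory rules concern other toxicities and do not settle how a skin or joint/muscle event should be handled, although they do show that dosing during an unresolved Grade 3 finding is not unique to this row. Whether another language version differs cannot be checked from the documents.

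It is also fair to say that *and* imposes a firm 7-day hold on events that recover early, which Table 9's first row does not. That floor follows the row's own stated minimum, and its cost is given under the fix.

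**Conclusion.** The concern holds as a minor safety-wording correction. As written, the Grade 3 row of Table 7 permits a lower-dose restart from day 7 on an unrecovered event, and no other text in Sections 5.3 or 5.3.2 prevents it. The difference in earliest restart is at most 21 days for late recovery and 6 for early recovery. This rests on a literal reading of *or*; it is not evidence that dosing on active Grade 3 toxicity was planned.

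The likely harm is limited. Restart is allowed rather than compelled, the dose is reduced, investigators may suspend, reduce or stop treatment at any time, and Section 6.6 allows unscheduled safety assessments.

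**What to change.** In the Table 7 Grade 3 row, replace *or* with *and* between the 7-day minimum and the recovery condition, so that both must be met, and keep the 28-day cap. Add that an event not resolved within 28 days follows the 28-day rule in Section 5.3.2. Leave the lower-dose restart bullet as it is. If the sponsor does intend a day-7 restart without recovery, the row should say so and state the conditions.

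The cost is one word, one cross-reference and a notice to the roughly 10 sites. Slowly resolving events may be held up to 21 days longer than the literal reading allows, and early-resolving events up to 6 days longer. Sample size, visit schedule and primary analysis method do not change. The same notice could clear up the two conflicting Grade 2 restart bullets.
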